- Allow Philips and/or regulatory agencies to inspect study facilities and pertinent records at reasonable times and in a reasonable manner that ensures subject confidentiality.
- Notify Philips as soon as possible if this study is to be inspected by a regulatory agency.
- Submit the proposed clinical investigation including the protocol and the consent form to an IRB for approval, if required.
- Ensure informed consent is obtained prior to the use of any test articles.
- Submit any proposed change in, or significant deviation from, the protocol to an IRB for approval, and ensure the changes are reflected in the informed consent form, as appropriate, and also approved by the IRB.
- Document protocol deviations and violations with explanations as appropriate.
- Submit Adverse Events to the Sponsor and IRB as outlined in the protocol.
- Submit timely progress reports to the IRB and Sponsor as appropriate.
- Maintain adequate and accurate records of all study procedures, observations, results, and other related information (such as safety, protocol compliance, and product accountability).

I agree that all information provided to me by the Sponsor including protocols, verbal and written information shall be kept confidential and restricted to the personnel involved in conduct of the trial. It is recognized that this information may be conveyed to the IRB. I also understand that reports or information about the trial and its progress shall not be provided to anyone not involved in the trial other than the Sponsor or other legally constituted authority.

Principal Investigator's Signature

Principal Investigator's Printed Name

 Protocol Study
 10649
 Document Title:
 Protocol Date:
 Page 5 of 18

 Number:
 Collaboration Live Clinical Study
 24Oct2019
 Page 5 of 18

3 Protocol Synopsis

Title:	Collaboration Live Clinical Study
Study ID:	US-GIS-Collaboration Live-2019-10649
Overview:	This study is being conducted to assess the use of Collaboration Live software in conferencing, sharing and remote control of the Philips EPIQ Series Ultrasound Systems.
Objectives:	The study will evaluate the performance and safety of the Collaboration Live software in a clinical setting.
Primary Endpoint:	Percentage of cases for which the remote control functionality performs in a clinically acceptable manner.
Study Design:	This is a prospective, single-arm clinical study of subjects who provide written consent. Subjects are scanned using a Philips EPIQ 5 or EPIQ 7 Ultrasound System equipped with Collaboration Live software. The study investigator will evaluate performance of the Collaboration Live tool with regard to performance of conferencing, sharing and control capabilities. Adverse events will be reported and the study investigator will assess potential relationship to the study device or study procedure. Additionally, the utility of Collaboration Live in remote consult of study patients will be evaluated. No patient follow-up beyond the initial consultation will be conducted with the Collaboration Live software solution.
Population:	30 subjects
Key Eligibility Criteria:	Subjects must be willing and capable of providing informed consent and participating in the study. Subjects must be indicated for a routine OB/GYN ultrasound examination at the site.
Sites:	1
Anticipated Study Duration:	3 months
Participant Duration:	Single visit (1 day)

4 Background Information

The Collaboration Live Clinical Study is intended to evaluate the performance and safety of the Collaboration Live software in a clinical setting and will enroll 30 patients scheduled for routine OB/GYN ultrasound exams. This is a prospective, non-randomized, single-arm clinical study. No patient follow-up is planned beyond the initial exam. The anticipated study duration is three months.

Ultrasound imaging is a form of medical imaging that involves the use of high frequency sound waves. Typically used to help a physician evaluate, diagnose, and treat patients, ultrasound imaging is minimally invasive and no radiation is involved. Collaboration Live is a software solution integrated into Philips EPIQ Ultrasound Systems that enables remote viewing, conferencing and control of the system. All study scanning (including scanning performed under remote control) will be conducted using the ALARA principle to ensure the safety of the subjects. As ultrasound imaging is based on non-ionizing radiation, it is generally considered safe when used by appropriately trained health care providers.

The use of Collaboration Live as part of the study does not significantly alter the risk profile of the Ultrasound System. A description of study risks is presented in Section 13, Risk and Benefit Analysis. Under 21 CFR 812.3(m), the Sponsor requests IRB determination of the study as a Nonsignificant Risk (NSR) Device Study. There is no specific benefit to individuals participating in the study.

Protocol	ol	Document Title:	Protocol Date:	
Study Number:	10649	Collaboration Live Clinical Study	24Oct2019	Page 6 of 18

The ethical principles for the treatment of human subjects on this study have their origin in the Declaration of Helsinki.

This study will be conducted according to the IRB-approved study protocol, ISO 14155 Clinical Investigation of Medical Devices for Human Subjects and applicable regional/national regulations.

Institutional Review Board (IRB) review and approval will be obtained, prior to consent and enrollment of any subject, and dispense of any test article. Any additional requirements imposed by the IRB or regulatory authority will be followed, if appropriate.

5 Product Description

Collaboration Live is a nondiagnostic software solution intended for use with Philips (Philips Ultrasound, [name]) EPIQ and Affiniti Series Ultrasound Systems (software version 5.0.2) that allows users to communicate (by text, voice, screen share, webcam video and remote takeover) from an ultrasound system or workstation to a remote destination.

With Collaboration Live, users may:

- Get real-time remote technical and application support from Philips.
- Confer remotely with peers during an exam.
- Share screens.
- Activate remote control of the screen, touch screen, and control panel.

5.1 Regulatory Status

The Collaboration Live software solution is considered investigational (i.e., has not been cleared by the FDA). For this study, the Collaboration Live feature will be evaluated as integrated into the EPIQ 5 and EPIQ 7 Ultrasound Systems (software version 5.0.2). The EPIQ Ultrasound Systems and supporting transducers used in the study have received FDA clearance and are indicated for use in obstetric and gynecological exams. The Philips EPIQ Ultrasound System is considered safe for use in human subjects in this clinical study because extensive safety testing has been conducted to confirm the safety profile and all hardware is FDA-cleared. The hardware complies with the following medical device safety standards listed in Table 5 below.

	Standard Name and Description
Electrical Safety	EN/IEC 60601-1:2006 + A1:2013 – Medical electrical equipment – Part 1: General requirements for basic safety and essential performance. The Philips EPIQ System has been designed and verified to comply with the electrical safety requirements of this standard, including requirements for electrical ground bond, leakage current, and dielectric withstand.
Electromagnetic Compatibility	EN/IEC 60601-1-2:2007 – Medical electrical equipment – Part 1-2: General requirements for basic safety and essential performance – Collateral standard: Electromagnetic compatibility – Requirements and tests. The Philips EPIQ System has been designed and verified to comply with the radiated and conducted emission requirements of this standard.
Usability	EN/IEC 60601-1-6:2010 – Medical electrical equipment – Part 1-6: General requirements for basic safety and essential performance – Collateral standard: Usability. The Philips EPIQ System has been designed and verified to comply with the usability requirements of this standard.

Table 5: Compliance with Medical Device Standards

Protocol		Document Title:	Protocol Date:	
Study Number:	10649	Collaboration Live Clinical Study	24Oct2019	Page 7 of 18

	Standard Name and Description				
Diagnostic Ultrasound Imaging	EN/IEC 60601-2-37:2007 – Medical electrical equipment – Part 2-37: Particular requirements for basic safety and essential performance of ultrasonic medical diagnostic and monitoring equipment. The Philips EPIQ System has been designed and verified to comply with the diagnostic ultrasound imaging requirements of this standard.				
Risk Management	EN/ISO 14971:2012 – Medical devices: Application of risk management to medi devices. The risk assessment and mitigation procedures for the Philips EPIQ System r been conducted in compliance with the requirements of this standard.				
Clinical InvestigationEN/ISO 14155:2011 – Clinical investigation of medical devices for human s clinical practice. This clinical study of the Philips EPIQ System with i Collaboration Live software is designed and conducted to comply with the human protections requirements of this standard. This compliance ensure investigations adhere to current Good Clinical Practice (GCP) guidelines.					
Device Labeling	EN/ISO 15223-1:2016 – Symbols to be used with medical device labels, labeling, and information to be supplied – Part 1: General requirements. The labelling associated with the Philips EPIQ System with investigational Collaboration Live software has been designed and verified to comply with the requirements of this standard.				

The use of Collaboration Live as part of the study does not significantly alter the risk profile of the Ultrasound System. A description of study risks is presented in Section 13, Risk and Benefit Analysis. Under 21 CFR 812.3(m), the Sponsor requests IRB determination of the study as a NSR Device Study. In addition, clinical readiness testing of the ultrasound system with investigational software will be performed prior to study initiation and will include an assessment of acoustic pressure and intensity output values to ensure thermal and mechanical indices remain below established FDA thresholds.

6 Study Design Rationale

The Collaboration Live Clinical Study is designed to demonstrate the safety and performance of the Collaboration Live software in a clinical setting. The results may be used to support global regulatory submissions and publication.

7 Study Objectives and Purpose

The study objective is to evaluate the performance and safety of the Collaboration Live software in a clinical setting. The study will assess the use of Collaboration Live in conferencing, sharing, and remote control of the Philips EPIQ 5 and EPIQ 7 Ultrasound Systems (software version 5.0.2) in performing routine OB/GYN ultrasound examination.

Collaboration Live is not intended to be used as a diagnostic tool. The clinical site's standard practices regarding image review and in-person consultation shall be followed as required to aid in diagnosis of medical conditions.

7.1 Endpoints and Additional Measures

The primary endpoint is the percentage of patient exams for which the remote control functionality performs in a clinically acceptable manner, where clinically acceptable is defined as:

- The system responds to the remote input as intended and without a delay interfering with the conduct of the exam. Additionally, a clinically acceptable exam would also result in no adverse events related to the control feature.

Protocol		Document Title:	Protocol Date:	
Study Number:	10649	Collaboration Live Clinical Study	24Oct2019	Page 8 of 18

Additional measures will be evaluated including:

- Adverse events, including investigator assessment of seriousness and relationship to the study device or study procedure
- Assessment of technical issues
- Success rates for key tasks in the collaborative exam
- Travel reduction attributable to use of Collaboration Live
- Ease of use
- User feedback regarding streaming, image quality and overall experience
- Patient feedback regarding remote consultation
- Impact of remote consultation on reimbursement

8 Study Design

This is a prospective, single-arm, clinical study and will enroll 30 subjects undergoing a routine OB/GYN ultrasound examination. No additional interventions or follow-ups to the subject will be conducted as part of the study.

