8.1.5 Ultrasound Exams: Remote Viewing and Remote Control

All subjects are indicated for a medically-necessary routine ultrasound exam and will undergo this exam as conducted by a qualified ultrasonographer. Using the Collaboration Live software installed on the ultrasound system, the study investigator will remotely view the exam, including images acquired, in real time. As necessary, the investigator may use the system's capabilities (including text, voice, screen share and webcam video) to provide feedback to the ultrasonographer. The investigator or delegates will also provide assessment regarding use of the Collaboration Live software on a 5-point (Likert) scale, including:

Protocol		Document Title:	Protocol Date:	
Study Number:	10649	Collaboration Live Clinical Study	24Oct2019	Page 9 of 18

- Streaming and image quality
- Ease of use
- Overall experience

The Collaboration Live software's remote control capability will also be used to adjust system settings during the exam. Systems settings may be adjusted by the investigator to assist in the following tasks:

- Image optimization (e.g., image depth, focal depth, gain)
- Pulsed-wave or Color Doppler Imaging
- M-Mode Imaging

To assess the primary endpoint, clinical acceptability, the investigator and qualified ultrasonographer will monitor the system response relative to input changes and record any adverse events occurring during remote control.

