8.1.6 Remote Patient Consult

Following the ultrasound exam, the investigator will use the Collaboration Live software's remote control capability to review acquired images with the patient and/or ultrasongrapher. The investigator will also consult the patient using the system's audio and video capabilities.

Study subjects will be asked to complete a Telemedicine Satisfaction Questionnaire to capture feedback regarding information related to use of the Collaboration Live software in remote patient consult. The time spent in the remote consult and the distance (in miles) between the patient and consulting physician will be recorded. Billing data will be evaluated to assess impact of remote consultation on reimbursement.

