8.1.7 Additional Measures

Additional information as assessed by the investigator or delegates will be reported throughout the exam, remote control evaluation, or remote consult, including:

- Adverse events, including seriousness and potential relationship to the study device or study procedure
- Technical issues using the Collaboration Live system
- Success rates for key tasks in the collaborative ultrasound exam, including:
 - Establishing remote connection
 - Establishing text chat
 - o Establishing voice call
 - Establishing webcam feed
 - Establishing screen share
 - Establishing remote control

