9.4 Withdrawal of Subjects

Study participation is voluntary. The subject may refuse to consent or may withdraw from the study at any time without penalty or loss of benefits to which he/she is otherwise entitled.

The Investigator may discontinue a study subject's participation in this study without his/her consent. If, in the opinion of the investigator, the health or safety of a subject is affected adversely by participation in the study, the subject will be removed.

Protocol		Document Title:	Protocol Date:	
Study Number:	10649	Collaboration Live Clinical Study	24Oct2019	Page 11 of 18

All subjects completing the study will be included in the primary endpoint analysis. No follow-up is required beyond the initial study visit and therefore, no loss to follow-up or withdrawal is anticipated. However, if subject withdrawal were to occur prior to evaluation of clinical acceptability, additional subjects will be enrolled to compensate for the withdrawn subjects.

10 Management of Subjects

The subject's involvement in the study includes the OB/GYN ultrasound exam, remote consultation and patient questionnaire. No study follow-up visits are planned.

There are no restrictions to patient participation regarding concomitant medications or treatments.

11 Assessment of Safety and Performance

The variables necessary for evaluation of the primary endpoint and additional measures are specified in the Table 11 below.

Endpoint or Additional Measure	Required Variables		
Primary Endpoint: Clinically Acceptable Performance of Remote Control Functionality	During remote control, it will be recorded whether the system responds to the remote input as intended and without a delay interfering with the conduct of the exam. Additionally, a clinically acceptable exam would result in no adverse events related to the control feature (see Adverse Events below).		
Adverse Events	Adverse events will be reported on the appropriate case report form. The investigator will assess the seriousness of the event and relationship of event to study device and study procedure.		
Assessment of technical issues	Device deficiencies will be reported on the appropriate case report form.		
Success rates for key tasks in the collaborative exam	Success of the following tasks will be recorded:		
	 Establishing the remote connection Establishing text chat Establishing voice call Establishing webcam feed Establishing screen share Establishing remote control 		

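### Can the adverse-event part of the primary endpoint be derived when relationship is recorded to device and procedure but not to the control feature?

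*Protocol*

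**What the plan says.** Section 7.1 defines the primary endpoint as the percentage of patient exams in which remote control performs acceptably. The system must respond as intended, without a delay that disturbs the exam, and "a clinically acceptable exam would also result in no adverse events related to the control feature". Among the additional measures, the same section lists "Adverse events, including investigator assessment of seriousness and relationship to the study device or study procedure". Section 8.1.7 repeats this as "Adverse events, including seriousness and potential relationship to the study device or study procedure".

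Section 8.1.5 has the investigator and the ultrasonographer watch the system response and "record any adverse events occurring during remote control". Section 8.1.6, which begins after the exam, has the investigator use the "remote control capability to review acquired images with the patient" or the ultrasonographer.

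Section 11 opens with "The variables necessary for evaluation of the primary endpoint and additional measures are specified in the Table 11 below". The primary endpoint row of that table restates the response and delay criteria and requires "no adverse events related to the control feature (see Adverse Events below"), so it points to the Adverse Events row. That row says: "The investigator will assess the seriousness of the event and relationship of event to study device and study procedure".

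Section 16 plans descriptive statistics only, with no hypothesis test, and tabulates Clopper-Pearson 95% intervals for 30 subjects.

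**The concern.** The endpoint turns on attribution to one function of the software, yet the row that Table 11 cross-references records attribution only to the whole device and to the procedure. Section 5 describes the software as also covering text, voice, screen share and webcam video, so a device-related event need not be a control-related one. Section 8.1.5 adds a criterion of timing instead of cause. Because remote control is used again in the consult, it is also fair to ask whether a problem there counts.

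Read this way, an exam could pass under one section and fail under another, and the choice would be made once the event was known. With 30 exams, a single reclassification visibly changes the reported rate.

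**Working it through.** **1. The failure rule.** Each place that mentions adverse events does a different job:

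| Place | Function | Wording on adverse events |
|---|---|---|
| 7.1, primary endpoint | Definition | Fails if related to the control feature |
| Table 11, primary endpoint row | Required variables | Same criterion |
| 8.1.5 | What staff record | Any event during remote control |
| 7.1 additional measures, 8.1.7, Table 11 Adverse Events row | General safety data | Relationship to device and procedure |

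Only the first two rows say what makes an exam fail, and they agree. Section 8.1.5 collects a wider set of events to which the definition is then applied; it does not say that every such event is a failure. Nor does the Adverse Events row say that a device- or procedure-related event fails an exam.

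**2. The delay criterion and the consult.** Section 7.1 and the primary endpoint row of Table 11 both limit a relevant delay to one that disturbs the exam. The opening of the Table 11 row, about remote control, says when the observation is made. The unit in Section 7.1 is the patient exam, its assessment is described in Section 8.1.5 on exams, and Section 8.1.6 starts after the exam. A delay in the consult therefore fails under neither text.

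**3. Where the missing category could matter.** Remote control is part of the study device, so a control-related event is also device-related. Hence:

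- No adverse event: every reading gives the same result.
- Event not device-related: not control-related, so the exam passes on this component under Section 7.1.
- Device-related event: the investigator must judge whether remote control or another function was responsible. Only here do the general categories not settle the answer.

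Section 13.2 names interruption of the procedure and exposure of patient data as the potential risks of the software. Neither is in itself an adverse event as Appendix 1 defines it, an untoward medical occurrence. An interruption during remote control would be judged under the response and delay criteria, which are recorded directly.

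**4. Size, if it happened.** Inputs from Section 16: n = 30, two-sided 95%, Clopper-Pearson. Lower limit = Beta(0.025; x, n − x + 1); upper limit = Beta(0.975; x + 1, n − x), or 100% when x = n. For x = 30 the lower limit reduces to 0.025^(1/30) = 88.4%, the protocol's own figure.

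| Acceptable exams | Rate | 95% interval |
|---|---|---|
| 30/30 | 100% | 88.4% to 100% |
| 29/30 | 96.7% | 82.8% to 99.9% |
| 28/30 | 93.3% | 77.9% to 99.2% |

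These match Table 16. One exam classified differently costs 88.4 − 82.8 = 5.6 points on the lower limit; two cost 88.4 − 77.9 = 10.5 points. The counts of one and two are assumed for illustration; the protocol gives no expected rate of such events.

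**The case for a change.** The best case for a change is that attribution is a judgement made when the event is recorded. A later analysis plan can define a derivation but cannot supply a judgement that nobody collected. Section 11 presents Table 11 as the necessary variables, its cross-reference leads to a row without the needed category, and no other section supplies it. Section 6 says the results may support regulatory submissions, and two differently classified exams would take the lower limit below the 80% mentioned in Section 16. One extra form item would be cheap.

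It stands that the Adverse Events row does not name the control feature. It does not follow that the judgement goes uncollected: the primary endpoint row lists that criterion under required variables, and the case report form, which is not shown, may hold the item. The 80% appears only in the description of the 30/30 result and is not a success criterion; in the two-exam case it is the lower limit, not the 93.3% rate, that falls below it. An explicit item would still be a causality judgement made after the event, so it would not remove that feature.

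Broader repairs would alter the endpoint. Restricting onset to the period of remote control would drop a control-related event that appears later. Adding the consult would extend an endpoint defined on exams. Counting every device- or procedure-related event during remote control would fail exams that Section 7.1 passes.

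**Conclusion.** The concern does not call for a change. There is one failure rule, stated consistently in Section 7.1 and in the primary endpoint row of Table 11, and the delay criterion is the same in both. What is left is a minor gap in the Adverse Events row. In a single-site study of 30 subjects, the investigator who operates the remote control and assesses relatedness can fill it by applying the Section 7.1 definition.

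The effect is nil if no device-related adverse event occurs, and 5.6 points on the lower confidence limit if one exam that would otherwise complete a 30/30 result is classified differently. No error rate or power is affected, since no test is planned. The conclusion assumes that Section 7.1 governs and that the attribution is made and documented with the event, as the required variables imply. Naming the control feature in the Adverse Events row would be harmless tidying, but the plan does not depend on it.
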